10.4 Other Completed Efficacy Analyses

10.4.1 Completed Change in Quality of Life assessed by TranQol and SF-36

TranQol:

The TranQol is a disease-specific, self-administered, well-validated health-related quality of life tool developed for beta-thalassemia patients (Klaassen, 2014; Klonizakis, 2017). The adult self-report version, used in this study, includes 36 questions assessed on a 5-point response, that are grouped into 5 domains (Physical Health, Emotional Health, Sexual Health, Family Functioning, School/Career Functioning). Scores are calculated according to author's guidelines and scoring rules (please refer to appendix 18.3.1 for calculation algorithms). Both the total score and the domain scores range from 0 (worst) to 100 (best).

To interpret the difference in change score from baseline (screening) between treatment groups and change score at the individual level, 2 threshold values are usually used: 1) the minimally important differences (MIDs), used as a benchmark to interpret mean score difference between groups as clinically meaningful in a clinical trial (FDA, 2006); and 2) the responder definitions (RDs), defined as the individual patient HRQoL score change over a predetermined time period that should be interpreted as a treatment benefit (FDA, 2009). Both thresholds have not yet been well established. However, data reported in literature seemed to suggest a change of 4–6 points in the total TranQoL score can be considered as the RD. However, as MIDs for the domains of the TranQoL are still not available from literature, $0.3*SD$ of the domain scores at baseline (screening) from the pooled data will be used as proxies for MIDs. The $0.5*SD$, which is generally considered as an approximation for RD (Norman, 2003; Norman, 2004) will not be used for MIDs because it is intended for differences in individual respondent scores rather than in group respondent scores, and there is an emerging consensus that the criterion of $0.5*SD$ is considered too high for MID (Maruish, 2011).

SF-36:

The SF-36 is a generic, self-administered instrument consisting of 8 multi-item scales that assess 8 health domains (Maruish ME, 2011; McHorney, 1994; Ware, 1992): Physical functioning (PF), Role-Physical (RP), Bodily Pain (BP), General Health (GH), Vitality (VT), Social functioning (SF), Role-Emotional (RE), Mental Health (MH). Two summary scales, Physical Component Summary (PCS) and Mental Component Summary (MCS), will be calculated using norm-based scores from the 8 health domains. The primary interests of the SF-36 are the 8 health domain scores and the PCS and MCS scores. Scores are calculated according to author's guidelines and

scoring rules (please refer to appendix 18.3.2 for calculation algorithms). The raw score for each health domain can be transformed into a 0 (worst) to 100 (best) domain score, which can be transformed into norm-based T-scores, with a mean of 50 and a standard deviation (SD) of 10. Higher norm-based T-scores indicate better health/QoL based on data from a nationally representative sample of adults from the US.

In order for one health domain scale to be meaningfully compared with the other scales and for domain scores to have a direct interpretation in relation to the distribution of scores in the US general population, the 0–100 scale score for each health domain can be converted to norm-based scores using a T-score transformation, with a mean of 50 and a standard deviation (SD) of 10. Higher norm-based T-scores indicate better health/QoL, based on data from a nationally representative sample of adults from the US. Two summary scales, the Physical Component Summary (PCS) and Mental Component Summary (MCS), in norm-based metric, can also be calculated from these eight health domains. The SF-36 has been thoroughly assessed, showing good psychometric properties.

Table 1 describes the range of possible T-scores, minimally important difference and responder definition for all SF-36 scale scores.

Table 1: Composition and Interpretation of T-Scores for SF-36 (Version 2) Component Summary Measures and Health Domain Scales

Scale/Measure	Composition	Range of Possible T-Scores		MID	RD
Physical functioning (PF)	Items 3a–3j	19.26	57.54	3.0	4.3
Role-physical (RP)	Items 4a–4d	21.23	57.16	3.0	4.0
Bodily pain (BP)	Items 7, 8	21.68	62.00	3.0	5.5
General health (GH)	Items 1, 11a–11d	18.95	66.50	2.0	7.0
Vitality (VT)	Items 9a, 9e, 9g, 9i	22.89	70.42	2.0	6.7
Social functioning (SF)	Items 6, 10	17.23	57.34	3.0	6.2
Role-emotional (RE)	Items 5a–5c	14.39	56.17	4.0	4.6
Mental health (MH)	Items 5a–5c	11.63	63.95	3.0	6.7
PCS	All scales	5.02	79.78	2.0	3.8
MCS	All scales	-3.33	80.09	3.0	4.6

MCS = Mental Component Summary; MID = minimally important difference; PCS = Physical Component

Summary; RD = responder definition

*Highest and lowest observed T-scores in 2009 general population normative sample

Statistical Analyses:

For both QOL endpoints, records beyond week 48 have been used.

The preselected primary domains of interest for the assessment are:

- TranQoL
 - Total score
 - Physical Health domain
- SF-36
 - Physical Functioning domain
 - General Health domain
 - Physical Component Summary

For the assessment of changes from baseline (screening), the analysis of scores at Week 24 has been considered as primary; [REDACTED]

[REDACTED]

To assess the extent of missing data at each assessment visit by treatment group, compliance rates for the TranQoL and SF-36 have been estimated on the ITT population separately based on the number of subjects included in the ITT population per treatment group who are eligible for assessment at a given scheduled visit.

Subjects have been considered compliant with completion of the TranQoL if at least 75% of the items are non-missing (ie, ≥ 27 items of the 36 items completed or non-missing total score) for a given assessment visit, and compliant with completion of the SF-36 assessment if at least half of the 36 items (ie, ≥ 18 items) are completed.

To assess the effect of luspatercept + BSC versus placebo + BSC on health-related QoL, the key analysis below has been performed based on the HRQoL evaluable population (Section 5.2.3).

To determine whether the findings of the primary analyses are generalizable to the entire ITT population, the comparability of the HRQoL evaluable and non-evaluable populations has been assessed at baseline (screening). The HRQoL non-evaluable population in this particular analysis has been defined as those subjects in the ITT population who are not included in both HRQoL-evaluable populations.

A cross-sectional analysis of change from baseline (screening) has been performed to compare the scores at Week 24 and Week 48 between treatment groups using ANCOVA models adjusted for baseline (screening) domain scores and randomization stratification factors. The least squares (LS) mean (95% CI and p-value) for changes from baseline (screening) at each post-baseline /screening visit in all domain scores within each treatment group, and the difference in the LS means (95% CI, p-value) between treatment groups at each post-baseline /screening visit have been estimated.

To avoid bias when interpreting differences between groups in HRQoL score changes from baseline (screening) to last QoL assessment, the corresponding treatment duration has been described per treatment groups for patients analyzed.

A number of sensitivity analyses, including analysis with imputation of missing data, were planned to assess the robustness of HRQoL findings from the main analysis and the impact of missing data.

Additional details of the highlighted analyses as well as sensitivity analyses, and additional analyses to assess subgroups and treatment effects on HRQoL were provided in a separate HRQoL statistical analysis plan, which has been finalized prior to database lock. The HRQoL statistical analysis plan has been appended to the separate specific HRQoL report.

The raw scores for each individual question and the calculated domain and component scores have been presented in the listings for TranQol and SF-36 respectively.

10.5 Other Extended Efficacy Analyses

In general, descriptive statistics will be provided and statistical tests will be applied if appropriate. For continuous variables, LS means with corresponding SEs for each treatment group, along with LS mean of treatment difference (luspatercept versus placebo) with corresponding 95% CI and p-value will be presented for ANCOVA method. Kaplan-Meier methods will be used to analyze time to event variables. Counts and percentages will be used to describe categorical variables. If an ANCOVA method is used, the statistical assumption will be validated first, log transformation will be applied as needed.

10.5.1 The Transfusion Reduction based on the Rolling Method

To measure the duration of transfusion burden reduction, time to the first erythroid response, transfusion independence and duration of transfusion independence, rolling method will be applied. The summary based on rolling method intends to reflect consistency with clinical practice. Please refer to Sections 10.5.7, 10.5.8, and 10.5.9 for more details.

The transfusion reduction will be measured using the consecutive “rolling” 12-week (or 24-week) time interval within the entire study period up to the efficacy cutoff, i.e., Days 2 to 85, Day 3 to 86 (or Day 2 to 169, Day 3 to 170 for 24-week) and so on. Note that, day 1 transfusion belongs to baseline. The transfusion reduction by 12-week is defined as subjects with $\geq 33\%$ (or 50%) reduction from baseline in RBC transfusion burden with a reduction of at least 2 units. The

transfusion reduction by 24-week is defined as subjects with $\geq 33\%$ (or 50%) reduction from baseline in RBC transfusion burden only (i.e., without considering the absolute unit reduction).

The treatment comparison with “rolling” method (luspatercept plus BSC versus placebo plus BSC) will be conducted by the CMH test stratified by the geographical regions defined at randomization as stratification factor. The OR (luspatercept versus placebo) with corresponding 2-sided (at 0.05 alpha level) 95% CI and p-value will be provided. The number and percentage of responders will be summarized by each treatment group and the difference in proportions (luspatercept – placebo) and corresponding 95% CI will also be calculated by exact unconditional test with “rolling” method as well.

A forest plot showing the ORs, 95% CI and p-value for the erythroid response (33% and 50%) in each subgroup will be provided with “rolling” method (by 12-week or 24-week respectively) as well.

A waterfall plot will be provided for the transfusion burden percent change from baseline during any 12-week or 24-week interval by treatment group respectively. Individual subject’s transfusion burden percent change from baseline will be displayed in a single bar. The displayed transfusion burden percent change is each subject’s largest percent decrease in transfusion burden during any post-baseline 12-week or 24-week interval.

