### **1.7.6. Interim Analysis (IA) – IA has been removed from the protocol**

Rationale:

The interim analysis has been originally implemented in the study to manage the timeline risk of the study if subject enrollment was very slow. As of 4 April 2017, 281 subjects have been randomized in the study, projected closure of randomizations is currently targeted in Jun 2017, which is approximately one year earlier than originally planned end of randomization. Current maintenance of high enrollment rates have diminished the purpose of the interim analysis, prompting to the decision to not perform the analysis and proceed to final analysis as per the study SAP. Subject safety is monitor on ongoing basis by independent DMC, thus removing the IA from the protocol, will not impact the already described regular safety monitoring in the protocol.

Revised Sections: Section 9.8 and Protocol Summary.

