- For RBC transfusion related efficacy endpoints summary beyond the 48-week double-blinded

treatment period, the 12-week interval is defined as:

Week 49 - 60 interval: from Day 338 to Day 421;
Week 61 - 72 interval: from Day 422 to Day 505;
Week 73 - 84 interval: from Day 506 to Day 589;
Week 85 - 96 interval: from Day 590 to Day 673;
Week 97 - 108 interval: from Day 674 to Day 757;
Week 109 - 120 interval: from Day 758 to Day 841;
Week 121 - 132 interval: from Day 842 to Day 925;
Week 133 - 144 interval: from Day 926 to Day 1009;
Week 145 - 156 interval: from Day 1010 to Day 1093;
Week 157 - 168 interval: from Day 1094 to Day 1177;
Week 169 - 180 interval: from Day 1178 to Day 1261;
Week 181 - 192 interval: from Day 1262 to Day 1345;
Week 193 - 204 interval: from Day 1346 to Day 1429;
Week 205 - 216 interval: from Day 1430 to Day 1513;
Week 217 - 228 interval: from Day 1514 to Day 1597.

All the data collected up to 11MAY2018 were used for summary in the primary CSR. The final database will be locked when everyone rolls over to a long-term follow-up study. All data collected up to the time of every subject rolling over to the long term follow up study will be used for summary. Data selection rules will be applied in each summary panel as needed, please refer to relevant sections for details.

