10. EFFICACY ANALYSIS

All efficacy evaluations are conducted using the ITT population, with the exception of Quality of Life analyses that are conducted on the HRQoL evaluable population. Statistical comparisons are made between luspatercept plus BSC vs. placebo plus BSC. Key secondary efficacy results are considered statistically significant after consideration of the strategy for controlling the family-wise Type 1 error rate, as described in Section 10.1, Multiplicity. All statistical tests are 2-sided at the significance level of $\alpha = 0.05$, and the corresponding p-values and 2-sided CIs for point estimates are reported, unless specified otherwise.

For the early treatment discontinued subjects, i.e., patients who did not complete 24 weeks or 48 weeks of double-blinded treatment period, the transfusion records were collected up to 48 weeks or 9 weeks post last dose, whichever was the later date. All the transfusion records collected throughout the entire study period up to the efficacy cutoff date were used in the RBC related efficacy analyses. The efficacy cutoff date for the primary CSR was defined as the minimum date among death date, study discontinuation date, last dose date + 20, and 11MAY2018. For the primary and key secondary endpoints, if at the time of data summary, a subject's efficacy cutoff date was before the end of the 12-week interval or a subject had any invalid transfusion records (i.e., transfusion unit not available) during the specified 12-week interval, this subject was included in the analysis as a non-responder.

All the efficacy analysis for the final CSR will not include the assessments for the placebo patients who crossed over to luspatercept. In other words, the assessments for the placebo patients will be analyzed up to the cross-over timepoint. For those subjects in the original luspatercept treatment, their assessments will be analyzed until the new efficacy cutoff date which is defined as the minimum date among death date, study discontinuation date, last dose date + 20.

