In the primary CSR, descriptive statistics for LIC measurements and change from baseline were summarized at week 24/48. The 24/48-week LIC change from baseline was analyzed using ANCOVA model with geographical regions defined at randomization and baseline LIC as covariates for the ITT population. Additionally, a shift table representing the shift from the baseline to week 24/48 category (≤ 3 ; $> 3-\leq 7$; $> 7-\leq 15$ and > 15) was provided for LIC. A subject has maximum two post-baseline LIC assessments (including “unscheduled”) during the 48-week double-blinded treatment period per protocol. If a subject has only one assessment, it is counted as “Week 48” visit; if a subject has two assessments, the first one is counted as “Week 24” visit, and the later one as “Week 48” visit regardless of the collected nominal visit name. This logic was used in the model based summary, change from baseline summary and the shift table summary for the primary CSR.

For the final CSR, descriptive statistics for LIC measurements and change from baseline will be summarized at weeks 24, 48, 96, 144, and 192. The 24/48/96-week LIC change from baseline will be analyzed using ANCOVA model with geographical regions defined at randomization and baseline LIC as covariates for the ITT population. Additionally, a shift table representing the shift from the baseline to week 24/48/96/144/192 category (≤ 3 ; $> 3-\leq 7$; $> 7-\leq 15$ and > 15) will be

provided for LIC. Post-baseline is defined as the closest visit at Weeks 24, 48, 96, 144 or 192 if the assessment is on or before the efficacy cutoff. If the assessment occurs after the efficacy cutoff, the assessment is not included in the reported visit. The efficacy cutoff is defined as min (death date, study discontinuation date, last dose date + 20). Only Weeks 24, 48 and 96 are analyzed for Placebo. This logic will be used in the summary, change from baseline summary and the shift table summary for the final CSR.

Additionally, bar plot was provided for baseline, week 24 and week 48 LIC categories (≤ 3 ; $>3-\leq 7$; $>7-\leq 15$; >15). Percent of subjects within each category were displayed by treatment group. No bar plots will be provided in the final CSR.

All the LIC data will be presented in a listing.

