- If the month and year of the incomplete stop date are the **same** as the month and year of the last dosing date, then the day of the last dosing date will be assigned to the missing day.
- If either the year of the partial date is **not equal to** the year of the last dosing date or the years of the partial date and the last dosing date are the same but the month of partial date is **not equal to** the month of the last dosing date, then the last day of the month will be assigned to the missing day.

Celgene Signing Page

This is a representation of an electronic record that was signed electronically in Livelink.
This page is the manifestation of the electronic signature(s) used in compliance with
the organizations electronic signature policies and procedures.

UserName: [REDACTED]
Title: [REDACTED]
Date: Thursday, 11 March 2021, 01:18 PM Eastern Daylight Time
Meaning: Approved, no changes necessary.
=====

UserName: [REDACTED]
Title [REDACTED]
Date: Friday, 12 March 2021, 12:42 AM Eastern Daylight Time
Meaning: Approved, no changes necessary.
=====

UserName: [REDACTED]
Title: [REDACTED]
Date: Friday, 12 March 2021, 10:22 AM Eastern Daylight Time
Meaning: Approved, no changes necessary.
=====

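### Four final-CSR between-arm tests (SAP 10.5.1, 10.5.8, 10.5.9, 10.5.10) compare arms with unequal follow-up and do not adjust for it

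*SAP*

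**What the plan says.** SAP Section 10 has two cutoff rules. In the primary CSR every subject in both arms ended at the earliest of death, study discontinuation, "last dose date + 20, and 11MAY2018". For the final CSR, "the assessments for the placebo patients will be analyzed up to the cross-over timepoint". For original luspatercept subjects, "their assessments will be analyzed until the new efficacy cutoff date", which is the earliest of death, study discontinuation and last dose plus 20 days, with no calendar date.

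SAP Section 2 explains that the future tense marks analyses updated in the final CSR. Four between-arm tests are written in that tense:

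1. **Rolling response (10.5.1):** CMH test of a 33% or 50% reduction in any rolling 12- or 24-week "time interval within the entire study period up to the efficacy cutoff".
2. **Transfusion independence (10.5.9):** CMH test of a transfusion-free spell in any rolling 6-, 8- or 12-week window up to the cutoff.
3. **Transfusion-event frequency (10.5.10):** negative binomial model for overall frequency, and for each 12-week interval as far as data go. The named terms are region and baseline frequency. No exposure term is named.
4. **Time to first response (10.5.8):** t-test in responders only.

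Protocol 9.6.3.9 bases time to response on double-blind data and makes it descriptive. The timeframe in protocol Table 2 for that endpoint ends at the last visit of the double-blind Treatment Period.

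**The concern.** Each test treats the arms as if they had been observed for the same time. A yes/no result over any window can only become more frequent as follow-up lengthens. A raw event count grows with time at risk. Late first responses can be seen only in the arm followed longer, so its mean among responders can move later. None of these needs a drug effect.

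The SAP guards against this elsewhere. Testing of LIC, BMD and myocardial iron stops at Week 96, and 10.4.1 describes treatment duration by arm so that last-assessment QoL differences are not misread. The four tests have no such protection.

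At stake is how the final CSR reads. It could show an inflated odds ratio for rolling response, together with a transfusion-event ratio above 1 for a drug that lowers transfusion need. Both would appear in the same report as the capped primary-CSR results, and the SAP plans no statement that the two sets are not comparable.

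**Working it through.** **1. How unequal follow-up can be**

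- Protocol amendment justification 1.7.6: "As of 4 April 2017, 281 subjects have been randomized in the study".
- From 4 April 2017 to the 11 May 2018 cap: 402 days / 7 = 57.4 weeks.
- The SAP approval stamp reads "Thursday, 11 March 2021". The lock was still to come, since SAP 5.1 says "The final database will be locked when everyone rolls over to a long-term follow-up study". From 4 April 2017: 1,437 / 7 = 205.3 weeks.
- Difference: 1,035 / 7 = 147.9 weeks.

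These are calendar times for a subject still on drug. The number who stayed on is not stated. First dose may follow randomization by up to 3 days (protocol 3.1.2), which changes little. SAP 10.5.2 shows the same gap: LIC is summarized to Week 192, but "Only Weeks 24, 48 and 96 are analyzed for Placebo".

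**2. The plan's own figure**

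The documents give no figure for this point. The sample size supplies the 200:100 split used below and reproduces: 40% versus 20%, 2:1, 90% power, two-sided 0.05, continuity-corrected, gives 90 placebo and 270 in total; 270 / 0.90 = 300.

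**3. Test 1, mechanism**

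Take the SAP's 20% placebo rate for one 12-week window and count non-overlapping blocks only. With k independent blocks, P(any response) = 1 − 0.8^k:

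- Week 96, k = 8: 1 − 0.168 = 83%.
- Week 228, k = 19: 1 − 0.014 = 99%.

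Correlation within subjects reduces this. For a beta-binomial with intraclass correlation ρ, P(none) = ∏(b+i)/(a+b+i), i = 0 to k−1, with a = 0.2(1−ρ)/ρ and b = 0.8(1−ρ)/ρ.

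| ρ | Any response by Week 96 | By Week 228 | Chance of p<0.05, no drug effect |
|---|---|---|---|
| 0.2 | 64% | 79% | 80% |
| 0.5 | 44% | 53% | 29% |
| 0.8 | 29% | 32% | 8% |

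**4. Test 1, simulated transfusion histories**

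Assumptions:
- 6–20 units per 24 weeks and no gap over 35 days (the eligibility rule); mean interval 14–28 days, SD 2–5 days, with or without slow drift.
- Five variability settings, with fixed Week 13–24 response off drug of 3–17%.
- Cross-over at 57–100 weeks. Luspatercept ends at Week 144, 192 or 228 (228 is the last interval tabulated in SAP 5.1, not known follow-up).
- Drop-out 10% or 20% per 48 weeks in both arms.
- 600 trials per scenario, CMH over three strata.

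| Luspatercept ends | p<0.05 with no drug effect, 33%/12-week |
|---|---|
| Week 144 | 15–32% |
| Week 192 | 23–52% |
| Week 228 | 29–67% |
| Common calendar cutoff | 3–6% |

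Other definitions gave 9–85% (50%/12-week) and 3–94% (33%/24-week, low where off-drug response is rare). With a real effect (40% extra early responders), the median odds ratio across settings rose from 1.9–3.0 with a common cutoff to 2.5–3.8.

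A second, simpler simulation without drop-out (unstratified two-proportion test, 2,000 trials) rejected in 65–94% with placebo to Week 72 and luspatercept to Week 228, in 38–76% for 96 versus 228, and in 5.0–5.4% with both at 72. Every false rejection under unequal follow-up favoured luspatercept.

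**5. Test 2, by assumed off-drug rate of a first 8-week transfusion-free spell**

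| Rate per year | p<0.05 with no drug effect |
|---|---|
| 0.2–0.5% | at most 1.5% |
| 1% | 3–11% |
| 2% | 9–28% |
| 5% | 24–64% |

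**6. Test 3**

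Without an offset, estimated ratio ≈ true rate ratio × (mean luspatercept follow-up / mean placebo follow-up). In the simpler simulation, mean events were 25.1 at Week 72 and 79.4 at Week 228: 79.4 / 25.1 = 3.16, and 228 / 72 = 3.17. With drop-out:

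| | Estimated ratio, no offset | With offset |
|---|---|---|
| True 1.0, Week 144 | 1.6–1.7 | 1.00 |
| True 1.0, Week 192 | 1.9–2.2 | 1.00 |
| True 1.0, Week 228 | 2.2–2.5 | 1.00 |
| True 0.8, all three | 1.3–2.0 | 0.80 |

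For single intervals with partly observed placebo subjects kept and a true ratio of 1.0, no offset gives 1.18 (Weeks 61–72), 1.27 (73–84) and 1.63 (85–96). With an offset it is 1.00–1.01.

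**7. Test 4**

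The result depends on when responses occur:
- Null transfusion histories: luspatercept significantly later in 48–94% of trials (for example 231 versus 115 days at Week 192), against 2–3% with a common cutoff.
- Constant hazard with luspatercept truly faster (40% versus 20% per 24 weeks): still significantly later in 20–44%.
- Responses concentrated in the first 18 weeks: later in under 2%.

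A log-rank test in all ITT subjects with censoring, under the null and the same unequal follow-up, rejects in 3–5%.

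**The case against.** - **Not all four are shown to be distorted.** Off-drug 8-week spells may be rare in subjects who entered with no gap over 35 days, and test 2 is then hardly affected. This stands as a condition on test 2.
- **Test 3 rests on silence.** Frequency could mean a rate, and an offset is not excluded. The SAP must therefore state the exposure term. The distortion follows only if raw counts are modelled.
- **Test 4 depends on response timing and works against the drug.** True. It cannot create a false efficacy claim, but the p-value would still be wrong.
- **Protocol Table 2 also marks time to response as Long-Term, and protocol 9.6.3 allows tests where appropriate.** The marking does not undo the double-blind timeframe in the same row, nor 9.6.3.9.
- **The capped primary-CSR results stay in the final CSR.** They do, and they can serve as the common-cutoff comparison. The updated p-values would still be produced.
- **A long window is intended.** For independence and event frequency it follows Table 2 and the extended objectives. The fault lies in the between-arm test, not in collecting or showing the data.
- **The sizes are assumed.** Follow-up, retention and within-subject correlation are not documented, and the plan's 10% drop-out has no time base. Since SAP 3.1 reports the primary objective met, the real-effect odds ratios are more relevant than the null rejection rates. This limits what can be said about size, not about the flaw.

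**Conclusion.** The concern holds. SAP Section 10 sets the unequal cutoffs explicitly, and the four tests are specified over them with no common window, exposure term or censoring. It should be fixed before the final CSR.

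Test 1 is the clearest case: its inflation always favours luspatercept, and is small only if within-subject correlation is very high or off-drug response is rare. Test 2 is affected in the same direction if off-drug independence is not rare. Test 3 works against luspatercept if raw counts are modelled. Test 4 can work against it, depending on response timing.

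The existence of the problem is certain from the text. The sizes rest on the assumptions listed. The primary and key secondary endpoints, and the primary-CSR versions of these four analyses, are not affected, and no confirmatory claim depends on the updated tests. The overall ICT-dose and ferritin ANCOVAs (SAP 10.5.3 and 10.5.4) also compare arms at different times on study. Their size was not assessed.

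**What to change.** 1. **Rolling response and transfusion independence:** limit between-arm CMH p-values to a common window, either the same calendar cutoff at unblinding or Week 48 in both arms. Report later luspatercept data descriptively. The 11 May 2018 results can serve as the comparison if the final CSR says so.
2. **Event frequency:** state the exposure term. Add log(days observed) as an offset to the overall model and to interval models with partial exposure. Omit between-arm tests for intervals without placebo data.
3. **Time to response:** drop the responders-only t-test and report descriptively on double-blind data, as protocol 9.6.3.9 and the Table 2 timeframe say. If a test is wanted, it would be an addition to the protocol: Kaplan-Meier and log-rank in all ITT subjects, with censoring, over the common window.

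The cost is SAP wording and minor reprogramming, with no new data. Some final-CSR between-arm p-values change, become descriptive or are dropped.
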